## **Appendix E. Quality of Life Questionnaires**

The following QoL questionnaires will be administered as part of this study, and copies of the questionnaires will be attached as an appendix of the protocol:

- Child Health Questionnaire - Parent Form 50 (CHQ-PF50; for pediatric participants) or Medical Outcomes Study Short Form Health Survey (SF-36; for adult participants)
- QoL questionnaires from within the IMACS activity and disease damage core set measure assessments include:
  - Childhood Health Assessment Questionnaire (CHAQ; for pediatric participants) or Health Assessment Questionnaire (HAQ; for adult participants)
- Calcinosis Assessment Tool (CAT), including Pain VAS
- Mawdsley Calcinosis Questionnaire
- The Patient Reported Outcomes Measurement Information System (PROMIS®) questionnaire will be used to capture daily life functions and health-related quality of life
- Skindex-29

## Appendix F. Screening Evaluation Form

The Screening Evaluation Form is included with the protocol submission to the IRB as a separate attachment.

SE

*Sodium Thiosulfate for Calcinosis*

### SCREENING EVALUATION (SE)

*For internal use only*

#### COMPLETION LOG

A2. Date Received    \_\_\_\_ / \_\_\_\_ / \_\_\_\_  
DD MMM YYYY

A4. Visit (Evaluation) Date: \_\_\_\_\_ / \_\_\_\_\_ / \_\_\_\_\_  
DD MMM YYYY

## I. STUDY INFORMATION

1. Participant type: a)  Adult

b)  Minor

2. Myositis type: a)  Dermatomyositis

b)  Juvenile Dermatomyositis (< 18 years at diagnosis)

## II. DEMOGRAPHICS

1. Gender: a)  Male b)  Female

2. Date of birth \_\_\_\_\_ / \_\_\_\_\_ / \_\_\_\_\_  
DD MMM YYYY

## III. COMMENTS

1. Comments on the case?  Yes  No

a. IF YES, please specify:

---

---

---

#### IV. INCLUSION CRITERIA

For these questions if the date is not known please leave the date field blank.

1.	Does the potential participant have documented symmetric proximal muscle weakness on exam, and if so what was the first date this was documented?	 Yes 1. ____ / ____ MMM YYYY	 No	 N/A
2.	Has the potential participant had an EMG? (skip question 2a if No)	 Yes	 No	
2a.	If so, does the potential participant have documented EMG evidence for myopathy, and if so what was the first date this was documented?	 Yes 2a. ____ / ____ MMM YYYY	 No	 N/A
3.	Does the potential participant have documented elevations of any of the following muscle enzymes (CK, LDH, AST, ALT or aldolase), and if so what was the first date this was documented?	 Yes 3. ____ / ____ MMM YYYY	 No	 N/A
4.	Does the potential participant have documented muscle biopsy evidence of polymyositis or dermatomyositis, and if so what was the first date this was documented?	 Yes 4. ____ / ____ MMM YYYY	 No	 N/A
5.	Does the potential participant have documented Gottron's papules or sign or Heliotrope rash on exam, and if so what was the first date this was documented?	 Yes 5. ____ / ____ MMM YYYY	 No	 N/A
6.	Considering 1-5 above, does the potential participant have documented criteria for probable or definite DM or JDM by the criteria of Bohan and Peter? (See criteria below this table.)	 Yes	 No	 N/A
7.	Is the potential participant at least 7 years of age?	 Yes	 No	
8.	Does the potential participant have extensive calcinosis (involving at least 2 extremities or the torso)?	 Yes	 No	 N/A
9.	Does the potential participant have a calcinosis activity VAS score of $\geq 3.5$ cm (out of 10 cm)?	 Yes	 No	
10.	Is the potential participant able and willing to undergo all study procedures and assessments, including receiving IV infusions?	 Yes	 No	
11.	a. What is the patient/parent global disease activity VAS score for this potential participant? _____ b. What is the physician global disease activity VAS score for this potential participant? _____ c. Are the potential participant's lab values for CK, LDH, aldolase, AST, and ALT all $\leq 2X$ ULN?  Yes  No d. In consideration of (a), (b), and (c), does the potential participant have myositis disease activity that is stable (i.e., both VAS scores $< 4$ cm and all available lab values $\leq 2X$ ULN)?	 Yes	 No	
12.	If taking any medications for myositis, has this treatment been stable for at least 6 weeks prior to study entry? (If not taking medications for myositis, mark N/A in right-hand column.)	 Yes	 No	 N/A
13.	If of reproductive potential, is the potential participant willing to use a reliable form of birth control for the 62-week duration of the study? (If not of reproductive potential, mark N/A in right-hand column.)	 Yes	 No	 N/A
14.	Is the potential participant or the potential participant's parent/legal guardian able and willing to give consent for the study?	 Yes	 No	

### **Bohan and Peter Criteria:**

1. Symmetric, often progressive, proximal muscle weakness
2. Characteristic electromyographic (EMG) triad
  - Short duration, small, low amplitude polyphasic potentials
  - Fibrillation potentials, seen even at rest
  - Bizarre high frequency repetitive discharges
3. Elevations of serum levels of muscle associated enzymes
  - - Creatine kinase (CK)
  - - Aldolase
  - - Lactate dehydrogenase (LD)
  - - Transaminases (ALT/SGPT and AST/SGOT)
4. Evidence of chronic inflammation in muscle biopsy:
  - - Necrosis of type I and type II muscle fibers
  - - Degeneration and regeneration of myofibers with variation in myofiber size
  - - Focal collections of interstitial or perivascular mononuclear cells
5. Characteristic rashes of dermatomyositis:
  - Scaly erythematous palpable eruptions over the metacarpophalangeal or interphalangeal joints, knees, elbows or medial malleoli (Gottron's papules)
  - - Erythematous macules over the metacarpophalangeal or interphalangeal joints, knees, elbows or medial malleoli (Gottron's sign)
  - - Periorbital or upper eyelid purplish discoloration (Heliotrope rash)

Definite disease = For DM any 3 of the first 4 criteria plus the rash

Probable disease = For DM any 2 of the first 4 criteria plus the rash

Possible disease = For DM any 1 of the first 4 criteria plus the rash

Juvenile disease = For DM any 2 of the first 4 criteria plus the rash

Adult disease = For DM any 1 of the first 4 criteria plus the rash

**Abbreviated Title:** Sodium Thiosulfate (STIC)

**Version Date:** July 07, 2023

## V. EXCLUSION CRITERIA

1.	Is the potential participant pregnant or breastfeeding? (If not a female of reproductive potential, mark N/A in right-hand column.)	 Yes	 No	 N/A
2.	Does the potential participant have any known allergies to sodium thiosulfate or its components?	 Yes	 No	 N/A
3.	a. What is the patient/parent global disease activity VAS score for this potential participant? _____  b. What is the physician global disease activity VAS score for this potential participant? _____  c. In consideration of (a) and (b), does the potential participant have severe myositis activity (i.e., either VAS score >4 cm)?	 Yes	 No	
4.	Has the potential participant had an escalation of immunosuppressive therapy in the past 2 months, including the addition of a new agent to treat the underlying disease or an increase in dose of an existing medication used to treat the patient's disease (other than an adjustment for weight or body surface area in children)? (If not taking immunosuppressive therapy, mark N/A in right-hand column.)	 Yes	 No	 N/A
5.	Does the potential participant have a current malignancy or a history of malignancy within 5 years of their diagnosis for JDM/DM (except for benign skin lesions or basal cell carcinoma)?	 Yes	 No	
6.	Does the potential participant have a known or suspected history of alcohol or drug abuse in the prior 6 months?	 Yes	 No	
7.	Does the potential participant have systemic lupus erythematosus, scleroderma, or a disease besides JDM/DM that is associated with calcinosis as a complication?	 Yes	 No	
8.	Has the potential participant had a change in any medications for the treatment of their calcinosis in the past 2 months? Medications include, but are not limited to alendronate, etidronate, pamidronate, probenecid, colchicine, diltiazem, thalidomide, and aluminum hydroxide. (If not taking medications for calcinosis currently or in the past 2 months, mark N/A in right-hand column.)	 Yes	 No	 N/A
9.	Has the potential participant taken any of the following medications in the past 2 months:  • Probenecid; • Diltiazem; • Aluminum hydroxide; • Hydrochlorothiazide?	 Yes	 No	

	Does the potential participant have current or a history of any of the following: 
 
• Heart failure;
 
• Renal impairment (GFR less than 30 representing severe renal disease);
 
• Liver disease (Child-Pugh class C);
 
• Arrhythmias (that are symptomatic or are concerning for progression to symptomatic arrhythmias);
 
• Recurrent kidney stones (more than one episode of symptomatic kidney stones separated by at least 1 month)?
 
	 Yes	 No	
10.	a. If $\geq 18$ years of age, does the potential participant have a T-score at or below -2.5 and one or more fractures?  ● Yes ● No	 Yes	 No	
11.	b. If $<18$ years of age, does the potential participant have a Z-score below -2 and one or more fractures?  ● Yes ● No	 Yes	 No	
	c. In consideration of (a) or (b), does the potential participant have severe osteoporosis (A yes for either answer above) or has he/she had a bone fracture in the past year?			
12.	a. Does the participant have a psychiatric illness or a history of medical noncompliance?  ● Yes ● No (mark N/A in right-hand column)	 Yes	 No	 N/A
	b. In consideration of (a), if yes, does the study team feel this will make the patient unlikely to complete the study?			
13.	a. Does the potential participant have dysphagia?  ● Yes ● No (mark N/A in right-hand column)	 Yes	 No	 N/A
	b. In consideration of (a), if yes, is it to a severity where non-oral feeding alternatives are needed to maintain adequate nutrition?			
14.	Does the potential participant require supplemental oxygen?	 Yes	 No	
15.	Has the potential participant experienced $>3$ episodes of cellulitis requiring IV antibiotics related to calcinosis within a year prior to enrollment, or had cellulitis within the prior month?	 Yes	 No	
16.	Has the potential participant ever taken sodium thiosulfate (previously or currently receiving)?	 Yes	 No	
17.	a. Is the potential participant currently taking oral prednisone or an equivalent oral corticosteroid dose?  ● Yes ● No (mark N/A in right-hand column)	 Yes	 No	 N/A
	b. In consideration of (a), if yes, is the dose more than 1 mg/kg/day?			

18.	Does the potential participant have any chronic infections that may make assessment of muscle disease difficult, including, but not limited to, hepatitis, HIV, HTLV1, or HTLV 2?	 Yes	 No	
19.	a. Complete Section VI (list of health conditions).  b. In reference to conditions listed in Section VI, does the potential participant have any health conditions that, in the opinion of the investigator, significantly increase the risk of taking sodium thiosulfate or participating in any of the study procedures?	 Yes	 No	 N/A
20.	a. What is the potential participant's weight (in kg)? _____  b. In consideration of (a), does the participant weigh less than 26 kg? (Note: We will attempt to enroll participants greater than 28 kg; participants weighing 26-28 kg may enroll, but will only complete some of the research blood work.)	 Yes	 No	
21.	a. Is the potential participant taking a regimen of pulse steroids or IVIG?  b. In consideration of (a), if yes, is this being taken at an interval other than every 1, 2, or 5 weeks?	 Yes	 No	 N/A
22.	a. If all inclusion criteria in Section IV have been met, and no other exclusion criteria in Section V have been met, then complete Section VII (list of concomitant medications).  b. In reference to concomitant medications listed in Section VII, and following a thorough assessment by the study PharmD, are any of the potential participant's concomitant medications thought to alter sodium thiosulfate's effects or pharmacokinetics? (If not taking any concomitant medications, mark N/A in right-hand column.)	 Yes	 No	 N/A

**Eligibility Determination:**

If the potential participant is at least 7 years of age, the criteria for probable or definite dermatomyositis are met, the responses to applicable inclusion criteria questions 6-16 are YES and all applicable exclusion criteria are NO, then the participant is eligible to participate.

## VI. LIST OF HEALTH CONDITIONS

In the space provided below, list all current health conditions of the potential participant and any additional comments (e.g., onset, severity, etc.).

Condition	Comments

## VII. LIST OF CONCOMITANT MEDICATIONS

In the space provided below, list all current medications the potential participant is taking, the dosing, and any additional comments (e.g., start date, duration of treatment, etc.). Include prescription and over-the-counter medications or dietary/nutritional supplements.

Medication, Dose	Comments
Prescription Medications:	
Non-Prescription Medications:	

**For Iothalamate Clearance? (if yes to either question, unable to undergo iothalamate clearance)**

**Is the patient allergic to Iodine?**

 Yes	 No	 N/A
--------------------------------------	--------------------------	---------------------------

**Does the patient have a history of asthma?**

 Yes	 No	 N/A
--------------------------------------	--------------------------	---------------------------

**VIII. ENROLLMENT OUTCOME**

1.	Participant is eligible for the study - all entry criteria met and no exclusions?	 Yes	 No	 N/A
----	---	--------------------------------------	--------------------------	---------------------------

Investigator Printed Name: \_\_\_\_\_

Signature of Investigator: \_\_\_\_\_

## **Appendix G. Script for Assessing Adverse Events for Weeks 10-24**

For adult participants, the following questions will be asked. If the answer is an affirmative additional information will be asked for to obtain more details including the timing of any events, severity, and the associated outcomes.:

Since you were last at the NIH have you had to go to the hospital for any reason and if so why?

Since you were last at the NIH have you had any fractures or broken bones?

Since you were last at the NIH have you had any nausea or lightheadedness?

Since you were last at the NIH have you developed any pain when you urinate?

Since you were last at the NIH have you had any headaches?

Since you were last at the NIH have you experienced any episodes of disorientation or confusion?

Since you were last at the NIH have you had any episodes where you had difficulty stopping bleeding?

**FOR FEMALE PARTCIPANTS ONLY:** Since you were last at the NIH have you become pregnant?

**FOR MALE PARTICIPANTS, ONLY:** Since you were last at the NIH have any of your sexual partners become pregnant?

Since you were last at the NIH have you developed or been diagnosed with any new medical problems?

Since you were last at the NIH have you had any surgeries?

Have there been any changes in your medical condition that we have not asked about that you believe we should know about and if so what are they?

Since you were last at the NIH have you had any side effects from the sodium thiosulfate ?

Is there anything else you think we should be aware of for the study in terms of your health?

For pediatric participants, the following questions will be asked. If the answer is an affirmative additional information will be asked for to obtain more details including the timing of any events, severity, and the associated outcomes.:

Since your child was last seen at the NIH has he or she had to go to the hospital for any reason and if so why?

Since your child was last seen at the NIH has he or she had any fractures or broken bones?

Since your child was last seen at the NIH has he or she had any nausea or lightheadedness?

Since your child was last seen at the NIH has he or she developed any pain when you urinate?

Since your child was last seen at the NIH has he or she had any headaches?

Since your child was last seen at the NIH has he or she experienced any episodes of disorientation or confusion?

FOR FEMALE PARTCIPANTS ONLY: Since your child last seen at the NIH has she become pregnant?

FOR MALE PARTICIPANTS, ONLY: Since your child was last seen at the NIH have any of his sexual partners become pregnant?

Since your child was last seen at the NIH has he or she had any episodes where he or she had difficulty stopping bleeding?

Since your child was last seen at the NIH has he or she developed or been diagnosed with any new medical problems?

Since your child was last seen at the NIH has he or she had any surgeries?

Have there been any changes in your child's medical condition that we have not asked about that you believe we should know about and if so what are they?

Since your child was last seen at the NIH has he or she had any side effects from the sodium thiosulfate ?

Is there anything else you think we should be aware of for the study in terms of your child's health?

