#### 10.1.2.1. Sodium Thiosulfate Treatment

Sodium thiosulfate injection solution, USP 12.5 g/50 mL [FDA Application Number: (NDA) 203923] has been approved in the US since 1992 and is indicated for sequential use with sodium nitrite for treatment of acute cyanide poisoning that is judged to be life-threatening (41). There have been no controlled clinical trials conducted to systematically assess the adverse events profile of sodium thiosulfate, and thus AE information reported in the medical literature was not collected using consistent

**Abbreviated Title:** Sodium Thiosulfate (STIC)

**Version Date:** July 07, 2023

monitoring or methodologies. Side effects that have been reported for sodium thiosulfate include osteoporosis, dental injury, hypotension, nausea, transient hypernatremia, transient hypertension and metabolic acidosis. This listing of adverse events involves a literature review, conversations with principal investigators involved in the studies described in table 2 where we were able to reach them, and from Adherex's briefing "Sodium Thiosulfate Injection, USP, 25% Briefing Document for The Pediatric Subcommittee of the Oncologic Drugs Advisory Committee" from November 1, 2011 presented to the FDA. Specific targeted monitoring for these side effects will be performed (see Section 14.3). Medications may be administered as needed to help alleviate these side effects. In particular, for participants who suffer from nausea with infusions, an option for pre-treatment with medications in order to prevent their nausea will be available. Patients experiencing fever, chills or hypotension may be premedicated with acetaminophen and/or Benadryl.

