### **14.3. Adverse Event Monitoring**

At each study contact, participants and/or their parents will be asked about any adverse events they have experienced. Any adverse events reported will be coded based on the Common Terminology Criteria for Adverse Events and logged.

The clinical site investigator will determine which events are associated with the use of study drug. For reporting purposes, an AE should be regarded as possibly related to the use of the investigational product if the investigator believes:

- There is a clinically plausible time sequence between onset of the AE and sodium thiosulfate administration; and/or
- There is a biologically plausible mechanism for sodium thiosulfate causing or contributing to the AE; and
- The AE cannot be attributed solely to concurrent/underlying illness, other drugs, or procedures.

An AE is deemed associated with the use of the study drug "if there is a reasonable possibility that the AE may have been caused by the drug" (21 CFR 312.32)

Known side effects of sodium thiosulfate include osteoporosis, hypotension, nausea, prolonged bleeding time, and metabolic acidosis. The development of kidney stones is a theoretical risk with the use of this medication. During treatment with sodium thiosulfate, we will perform specific targeted monitoring for these side effects as follows:

**Abbreviated Title:** Sodium Thiosulfate (STIC)

**Version Date:** July 07, 2023

- Osteoporosis will be monitored by DEXA scan at week 0, 6, 10, 24, and 62 for changes in bone mineral density. Height will also be measured for loss of stature.
- Blood pressure will be monitored before and after infusions to evaluate for alterations of blood pressure. It will be monitored every 30 minutes during the infusion and if the patient develops any symptoms.
- Nausea will be evaluated by patient reports.
- Prolonged bleeding time will be monitored by weekly laboratory evaluation of prothrombin time (PT) and partial thromboplastin time (PTT) from weeks 0 to 10 during the infusions.

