**Table 8 Targeted Safety Monitoring Assessments**

	Inpatient Period - STS Infusions Given 3x Weekly			Follow-up Visits	
	Week 0	Week 6	Week 10	Week 24	Week 62
DEXA for osteoporosis	X a	X	X	X	X
Blood Pressure	X – taken before and after each infusion from Week 0 to Week 10				
Nausea	X – evaluated continually by patient report from Week 0 to Week 10				
PT/PTT	X – performed once per week from Week 0 to Week 10				
Renal Ultrasound		X		X	X
Electrolytes, venous blood gas	X – performed once per week from Week 0 to Week 10				

a. If a DEXA scan has been performed within 6 months prior to initiation of the study, that will be used as the baseline DEXA evaluation

*Abbreviated Title:* Sodium Thiosulfate (STIC)

*Version Date:* July 07, 2023

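### Dental injury is listed as a reported side effect with targeted monitoring promised in Section 14.3, but neither Section 14.3 nor Table 8 has a dental measure, so a clean dental result would be weak evidence of absence

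*Combined protocol and SAP*

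**What the plan says.** Section 10.1.2.1 states: "Side effects that have been reported for sodium thiosulfate include osteoporosis, dental injury, hypotension, nausea, transient hypernatremia, transient hypertension and metabolic acidosis". Two sentences later it commits to checks on all of them: "Specific targeted monitoring for these side effects will be performed (see Section 14.3".

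Section 14.3 starts from another list: "Known side effects of sodium thiosulfate include osteoporosis, hypotension, nausea, prolonged bleeding time, and metabolic acidosis". It adds kidney stones as a theoretical risk and then limits the targeted checks to its own list: "During treatment with sodium thiosulfate, we will perform specific targeted monitoring for these side effects as follows". The checks that follow are DEXA and height, blood pressure, nausea by patient report, PT/PTT, electrolytes with venous blood gas, and renal ultrasound. The table headed "Table 8 Targeted Safety Monitoring Assessments" has the same content apart from height. Neither place mentions teeth.

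Section 14.3 also provides a general inquiry: "At each study contact, participants and/or their parents will be asked about any adverse events they have experienced". Table 4 schedules formal adverse-event review at Weeks -10, -4 and 0, weekly during treatment, and at Weeks 24 and 62. It also has a review-of-systems row, every two weeks during infusion.

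Section 5.3 sets a minimum physical exam: heart, lungs, abdomen, skin, joints and muscle strength. Appendix G scripts the two contacts between Weeks 10 and 24. It asks by name about hospital visits, fractures ("Since you were last at the NIH have you had any fractures or broken bones"), nausea or lightheadedness, painful urination, headache, confusion, bleeding, pregnancy and surgery. It then asks openly about new medical problems, side effects of the drug, and anything else.

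**The concern.** The safety plan promises something in one section that the section it points to does not deliver. Safety of ten weeks of treatment in children and adults is a secondary objective (Section 2), and adverse-event incidence and severity is a secondary outcome (Section 2.1). If the final report says no dental injury was seen, a reader of Section 10.1.2.1 would take that as the result of a directed search, but no directed search is written down.

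The allocation of effort is also hard to follow. Section 10.1.2.1 later calls osteoporosis a theoretical risk that has never been reported, and Section 14.3 calls kidney stones theoretical. Both have scheduled imaging. Dental injury, listed as reported, has no measure.

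**Working it through.** **Step 1: match each listed effect to a measure.** The effects come from Section 10.1.2.1, the measures from Section 14.3 and Table 8.

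| Listed effect | Targeted measure |
|---|---|
| Osteoporosis | DEXA at Weeks 0, 6, 10, 24, 62; height |
| Hypotension | Blood pressure around and during infusions |
| Transient hypertension | Same blood pressure readings |
| Nausea | Patient report |
| Transient hypernatremia | Electrolytes, at least weekly |
| Metabolic acidosis | Electrolytes and venous blood gas, at least weekly |
| Dental injury | None |

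Six of seven have a measure. Hypernatremia and hypertension are also missing by name from the Section 14.3 list, but its measures would pick them up. Only dental injury has neither a name nor a measure there.

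**Step 2: look for a measure elsewhere.** The minimum exam in Section 5.3 does not name the mouth. CT covers trunk and extremities (Section 5.8), MRI/PET starts at the skull base (Section 5.9), and no imaging section names teeth as a target. Neither version of the Appendix G script has a dental question. What remains is the general adverse-event inquiry, the review of systems and the scripts' open items.

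**Step 3: what a zero count would show.** The plan states no figure to reproduce. The documents give 18 as the enrollment ceiling and 13 as the completer target. The number treated is not fixed, so both are shown. The true rate *p* and the captured fraction *s* are my assumptions.

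- One-sided 95% upper bound after zero events with full capture: 1 − 0.05^(1/n). For n = 18 this is 15.3%; for n = 13 it is 20.6%.
- With capture *s* the bound on the true rate is that value divided by *s*. For n = 18: 0.153/0.5 = 30.7% and 0.153/0.25 = 61.3%, from unrounded values. For n = 13: 41.2% and 82.3%.
- Chance that no event is recorded: (1 − p·s)^n. For n = 18 and p = 10%: 0.90^18 = 0.150, 0.95^18 = 0.397, 0.975^18 = 0.634.

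| Assumed true rate | n | s = 1 | s = 1/2 | s = 1/4 |
|---|---|---|---|---|
| 5% | 18 | 40% | 63% | 80% |
| 10% | 18 | 15% | 40% | 63% |
| 20% | 18 | 2% | 15% | 40% |
| 5% | 13 | 51% | 72% | 85% |
| 10% | 13 | 25% | 51% | 72% |
| 20% | 13 | 5% | 25% | 51% |

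The s = 1 column is an ideal. A direct question would move capture toward it, by an amount the documents do not let anyone state.

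**The case against.** A reader might infer that a clean dental result would mean only that nobody asked. The documents do not support that. Participants are asked about any adverse event at each contact, the review of systems recurs through treatment, and both scripts end with several open questions. Section 13.1 has every observed or reported event recorded. A tooth problem that a participant mentions would be captured.

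Nor can a dental check be ruled out altogether. Section 5.3 sets a minimum and leaves exam details to the Manual of Procedures, which is not among the documents. The content of the review of systems is not given either.

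The two lists differ in other ways, which suggests they were never reconciled rather than that teeth were singled out. Appendix G is a secondary place for the gap: it serves two contacts after treatment, whereas the targeted monitoring in Section 14.3 is for the treatment period. The documents give no dental frequency or mechanism. The list in Section 10.1.2.1 is itself loose, since it includes osteoporosis and the same section later says osteoporosis was never reported. One should not infer that the drug is known to damage teeth.

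All of that stands. It does not repair the reference: general questions are not the specific monitoring that Section 10.1.2.1 promises. The open items also ask the participant to attribute a tooth problem to the drug, or to regard it as medical, before mentioning it.

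**Conclusion.** The point holds as a mismatch between Section 10.1.2.1 on one side and Section 14.3 and Table 8 on the other. In the available text dental injury is the only one of the seven listed effects without a targeted measure. Zero recorded dental events would depend on open questions and an unspecified review of systems, and would be weak evidence that no harm occurred.

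The size cannot be fixed from the documents. The 10% rate, the half and quarter capture, and 18 treated are assumptions for illustration. The 15.3% bound applies to any event never seen in 18 participants; better questioning does not shrink it, but incomplete capture makes it too optimistic. The primary outcome is unaffected. This should be corrected because the promise is explicit, the trial is small and the correction is cheap.

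**What to change.** Reconcile Section 10.1.2.1, Section 14.3 and Table 8 by adding dental injury to the Section 14.3 list and to Table 8.

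Add one direct question, such as whether there has been any new tooth problem (chipped, broken, loose or painful) since the last review. Ask it at the existing adverse-event reviews and in both Appendix G scripts. Include the reviews at Weeks -4 and 0, so that the lead-in, nominally the same ten weeks as treatment, provides a comparator. Section 8.1 plans McNemar tests for adverse-event incidence, and a paired comparison between periods needs the same question in both.

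A brief look at mouth and teeth within the existing physical exam is optional. If the Manual of Procedures already has one, cite it in Section 14.3.

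While editing Appendix G, correct a clerical slip in the pediatric version: "Since your child was last seen at the NIH has he or she developed any pain when you urinate" asks the parent about the wrong person.

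The cost is one question per contact, a line in Section 14.3 and a row in Table 8, with no new visit, staff or test. Some background dental events will probably be recorded; the pre-treatment answers help to interpret them.
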